ICH: International Conference on Harmonisation

IECSCYL: Instituto de Estudios de Ciencias de la Salud de Castilla y León

IQR: InterQuartil Range

NFCL: Cutaneous Femoral Nerve Lateral

NVPO: Postoperative Nausea and Vomiting

PAINAD: Paint Assessment in Advanced Dementia

PENG: PEricapsular Nerve Group

SatpO2: Peripheral Oxygen Saturation

SEDAR: Spanish Society of Anesthesiology, Resuscitation and Pain Therapeutics TA:

Blood Pressure

URPA: Post-Anesthetic Reuperation Unit

1. SUMMARY AND GENERAL INFORMATION

1.1. TYPE OF APPLICATION

Non-commercial Phase IV clinical trial of low level of intervention.

1.2. IDENTIFICATION OF THE SPONSOR

Fundación Instituto de Estudios Ciencias de la Salud de Castilla y León (IECSCYL)-Instituto de Investigación Biomédica de Salamanca (IBSAL).

IECSCYL-IBSAL Foundation.

1.3. TITLE OF THE CLINICAL TRIAL

Phase IV clinical trial randomized and controlled on the analgesic efficacy of the combined block (PENG - pericapsular nerve group- and the femoral lateral cutaneous nerve) in hip fractures of the elderly. Comparative study between Levobupivacaine and Ropivacaine.

1.4. PROTOCOL CODE

PENG-CAD.

1.6. CENTRES WHERE THE STUDY IS PLANNED

University Care Complex of Salamanca.

1.7. CEIM

Ethics Committee of Research with Medicines Health Area of Salamanca.

1.9. DESCRIPTION OF THE STUDY PRODUCTS

Group R (Ropivacaine), Group L

(Levobupivacaine) Route of administration:

perineural ecoguided.

1.10. CLINICAL TRIAL PHASE

Phase IV of low level of intervention.

10.11. OBJECTIVES

Main: To compare the analgesic efficacy of both local anesthetics in the regional blockade of hip fracture surgery in the elderly.

Secondary: 1) Describe the behavior of this combined technique in hip fractures, establishing latency of onset and duration of analgesia.

2) Describe the side effects derived from the described combined technique.

1.12. STUDY DESIGN

Prospective clinical trial (phase IV) of low level of non-commercial intervention, comparative of balanced, randomized groups, to compare the analgesic efficacy of the local anesthetics Ropivacaine and Levobupivacaine in peripheral nerve block in hip fracture surgery of the elderly.

1.13. STUDY DISEASE

The hip fracture of the elderly, subjected to both partial prostheses and endomedullary nailing.

1.14. STUDY VARIABLES

A. Main endpoint: duration of nerve block (analgesic efficacy of the two local anesthetics).

B. Secondary variables:

1. analgesia latency
2. duration of analgesia
3. adverse effects of the drugs used
4. scores of the analgesic scales: EVN, Algoplus, PAINAD.

1.15. STUDY POPULATION AND TOTAL NUMBER OF PATIENTS

Patients over or equal to 65 years of age who are going to undergo hip surgery for fracture.

The necessary sample size will be 108 patients, 54 patients per branch (Ropivacaine and Levobupivacaine), assuming 10% of losses.

1.16. DURATION OF PROCESSING

The duration of the treatment of each patient will be considered until the evaluation of the analgesic scale corresponding to the 48 h of the performance of the procedure. Patients may also be discontinued from the study at the discretion of the investigator at an earlier time or if they withdraw their consent at any time.

1.17. CLINICAL TRIAL SCHEDULE

From October 2020 until full recruitment. Approximately 15 patients/month will be recruited, which would mean a total of 7 months, that is, until April 2021.

2. INTRODUCTION

The increase in life expectancy together with very low birth rates is causing an accelerated growth in the percentage of older people, which results in an increase in the aging of the population, especially in the industrialized world. In our country, the phenomenon of aging is even more accelerated, since in less than 30 years the number of people over 65 years of age has doubled. Current data in Spain show that the population over 65 years of age is around 17% of the total population, with more than 7 million people (National Institute of Statistics-INE, 2008), of which approximately 25% are octogenarians. As a consequence, it is increasingly common to find in clinical practice elderly patients who require treatment of diseases and complications that are typical of advanced age.

Among these is the hip fracture, which presents a serious problem of morbidity and mortality for patients, and has a great impact on health costs due to both its treatment and the complications derived. It is estimated that there are 1.6 million fractures per year worldwide, with more than 610,000 fractures per year in Europe, and in Spain 45,000 fractures occur annually in older people(1, 2) of 65 years, being 80% over 75 years of age and with an associated annual mortality of about 30%(3, 4). Hip fracture is one of the most frequent surgical diagnoses in our environment. A very old and multipathological population, generally polymedicated and in which the presence of neurodegenerative diseases is not uncommon, makes it a very fragile population, which can sometimes have difficulty expressing its feelings, including pain, which is usually underdiagnosed(5). We must offer these patients an effective analgesic treatment from the first moment, avoiding the use of opioids and any drug that may deteriorate their cognitive faculties, and minimizing the use of usual analgesics (some of them, such as NSAIDs, can affect the control of blood pressure and already decreased renal function). Pain control in these patients is very important because it facilitates post-surgery recovery and early mobilization, and reduces the time of hospitalization after surgery, and the appearance of complications such as delirium, infections or thromboembolism(6). In addition, it accelerates the initiation of rehabilitation and functional recovery of elderly patients.

The debate on the most appropriate anesthetic technique for the surgery of the hip fracture of the elderly is still valid, between general and neuraxial anesthesia(7-11), as well as the different peripheral blocks combined or not with general or neuraxial anesthesia(12-16). Different anesthetic techniques have been used, such as femoral nerve block -BNF-, iliac fascia compartment block -BCFI-, lateral cutaneous femoral nerve block -NFCL-, among others. Although all of them have been shown to be effective in the surgery of the hip fracture of the elderly, they are insufficient in analgesic control.

Pain is a problem of special relevance in the elderly patient. It is estimated that between 50-80% of those over 65 years of age suffer some type of pain(17). Due to the presence of pluripathology and functional impairment, they become patients of great fragility who may also have cognitive impairment associated with them. In this type of patients the assessment of pain becomes complicated, being of enormous importance to be able to make a correct approach to the patient and achieve an adequate analgesic control. To all this, it is added that all scales and questionnaires have limitations, being convenient the assessment of more than one for the correct evaluation of the painful process(18-21). Thus, we will use 3 assessment scales: Visual Numerical Scale (EVN), Algoplus Scale (ALGSC), and Paint Assessment in Advanced Dementia Scale (PAINAD).

Since 2018, it has become popular to perform a technique known as PENG (pericapsular nerve group) that, because it affects only sensory endings, should not cause any degree of motor block of the affected nerves(22-25). This last aspect is of special interest, since muscle weakness due to femoral nerve block has traditionally been responsible for patients' falls when they begin postoperative ambulation.

Despite evidence that peripheral nerve blocks, and PENG in this case, are beneficial to the patient, neither adequate doses nor local anesthetic (AL) have been determined(13, 23, 24, 26, 27).

2. JUSTIFICATION OF THE STUDY

2.1. RELEVANCE OF THE STUDY

The realization of the PENG technique for the surgical management of the hip fracture of the elderly, has been incorporated into the usual practice, because it offers an adequate analgesia for the mobilization of the patient, makes it necessary to have a lower dose of local anesthetic in the spinal block, and achieves a correct postoperative analgesia, allowing the early mobilization of the patient without pain. Although performing surgery requires the help of other anesthetic techniques, peng blockade allows us to use fewer doses of anesthetics intrathecally, which translates into better hemodynamic stability, both intra and postoperative. Likewise, the postoperative analgesia that it produces will avoid the consumption of concomitant analgesia, avoiding pharmacological interference, with less risk of toxicity, both hepatic and renal.

We have at our disposal different local anesthetics that can be used in the nerve block, and, although with a series of common characteristics, they differ in some pharmacological aspects, which can be translated into the cynical one in that the selection of a certain local anesthetic can have an impact on the time of initiation of surgery, in which better or worse analgesic control is achieved, and in which the duration of said analgesic is greater or lesser duration and intensity in the postoperative period.

However, there is no scientific evidence of which local anesthetic is appropriate, nor what would be the ideal doses that would produce the balance between good analgesic control and minimal side effects.

In addition, it is intended to validate the assessment of pain in the elderly by combining three scales: EVN, Algoplus, PAINAD.

2.2 STUDY DRUGS

2.2.1 ROPIVACAINE

Ropivacaine is a long-acting local amide-type anesthetic with both analgesic and anesthetic effects, approved in our country since March 2012. At high doses it produces surgical anesthesia, while at low doses it causes a sensory block accompanied by a limited and non-progressive motor block.

The mechanism is a reversible reduction of the permeability of the nerve fiber membrane to sodium ions. As a consequence, the rate of depolarization decreases and the threshold necessary to produce excitation is increased, resulting in a local blockage of nerve impulses.

The most characteristic property of ropivacaine is the prolonged duration of action. The onset and duration of action of local anesthetic efficacy depends on the site of administration and dose, but are not influenced by the presence of a vasoconstrictor agent (e.g. adrenaline (epinephrine)).

Ropivacaine is indicated in the treatment of acute pain in adults and adolescents over 12 years of age in: Continuous epidural perfusion or intermittent bolus administration during the postoperative period or in labor pain; Peripheral blocks; and Continuous peripheral nerve block by continuous infusion or intermittent bolus injections, e.g. treatment of post-surgical pain.

For the treatment of postoperative pain, ropivacaine can be used for epidural block using an epidural catheter, so that adequate analgesia can be achieved with only a slight and non-progressive motor block in most cases of postoperative pain with a moderate to severe character. The maximum duration of the epidural block is 3 days, and a significant reduction in the need to use opioids has been observed. It can also be used in association with fentanyl for the treatment of postoperative pain for a period of up to 72 hours. The combination of Ropivacaine and fentanyl may provide better pain relief, but cause side effects of opioids.

Ropivacaine is well tolerated and does not require adjustment in patients with impaired renal function when administered for single-dose or short-term treatment. It is metabolised in the liver and should therefore be used with caution in patients with severe liver disease. Cytochrome P450 (CYP) 1A2 is involved in its metabolism, so potent CYP1A2 inhibitors, such as fluvoxamine and enoxacin, may interact with Ropivacaine and concomitant use should be avoided.

The adverse reaction profile of Ropivacaine is similar to that of other long-acting local amide-type anaesthetics and varies by route of administration. The most frequently reported adverse reactions, nausea and hypotension, are very common during anesthesia and surgery in general and it is not possible to distinguish those produced by the clinical situation from those caused by the drug or blockage. In addition, common adverse reactions of paresthesias, dizziness, headache, bradycardia, tachycardia, hypertension, vomiting, stiffness, back pain, urine retention, temperature elevation, and chills have been reported.

2.2.2 LEVOBUPIVACAINE

Levobupivacaine is a long-acting local amide-type anesthetic with both analgesic and anesthetic effects, approved in our country since November 2013.

It works by blocking nerve conduction in sensory and motor nerves largely due to interaction with cell membrane voltage-gated sodium channels, but also blocks potassium and calcium channels. In addition, Levobupivacaine interferes with impulse transmission and conduction in other tissues where effects on the cardiovascular and central nervous systems are the most important for the occurrence of clinical adverse reactions. The dose of Levobupivacaine is considered equipotente with bupivacaine.

Levobupivacaine is indicated in adults in Major Surgical Anesthesia (e.g. epidural, intrathecal, peripheral nerve block) and Minor (e.g. local infiltration, peribulbar block in ophthalmic surgery) and for the treatment of pain (in continuous epidural perfusion, single or multiple bolus epidural administration for the treatment of pain, especially post-surgical pain). In analgesia (e.g. epidural administration for the treatment of pain) the lowest concentrations and doses are recommended. When deep or prolonged anaesthesia with complete motor block (e.g. epidural or peribulbar block) is required, the highest concentrations may be used. Careful aspiration is recommended before and during injection to avoid intravascular injection.

The maximum dose should be determined by assessing the size and physical condition of the patient, along with the concentration of the drug and the area and route of administration. There is an individual variation in the onset and duration of the block. Experience gained in clinical trials shows that sensory block suitable for surgery occurs within 10-15 minutes after epidural administration, with a regression time in the range of 6-9 hours. In the treatment of post-surgical pain, the dose administered during surgery should be taken into account. When used for regional major nerve block, the lowest effective dose of local anesthetic should be used to avoid high plasma levels and serious adverse reactions.

There are no relevant data on Levobupivacaine in patients with hepatic impairment, although it is metabolised in the liver, and should be used with caution in patients with liver disease or reduced hepatic blood flow. Levobupivacaine is extensively metabolized without detecting unchanged Levobupivacaine in urine or feces.

There are no data in patients with renal impairment. It should be used with caution in debilitated patients, elderly patients or acute patients, and also in patients receiving antiarrhythmic drugs with local anaesthetic activity (e.g. mexiletine, or class III antiarrhythmic drugs) because its toxic effects may be additive.

Experience on the safety of treatment with Levobupivacaine for more than 24 hours is limited. The adverse reaction profile of Levobupivacaine is similar to that of other local amide-type anesthetics. Adverse reactions with local amide-type anesthetics are rare, but may occur as a result of overdose or unintentional intravascular injection and may be serious. Some adverse reactions reported are very common during anaesthesia and surgery in general and it is not possible to distinguish those caused by the clinical situation from those caused by the drug or blockage. The most commonly reported adverse reactions are nausea and vomiting, hypotension, dizziness, headache, fever, pain during the procedure, or back pain. Cases of prolonged weakness or sensory disorders, some of which have been permanent, have been reported associated with treatment with Levobupivacaine. It is difficult to determine whether the long-term effects were the result of drug toxicity or unnoticed trauma during surgery or other mechanical factors, such as catheter insertion and manipulation.

2.3. JUSTIFICATION OF THE SELECTED VARIABLES

There are several studies that try to identify the ideal anesthetic for the management and control of pain from hip fracture surgery in the elderly. The optimal thing would be to use an anesthetic with the lowest possible latency, since this will favor the start of surgery. And, at the same time, with a more lasting analgesia with the least motor involvement. Therefore, it is essential to collect efficacy data (effective blockade that allows us to mobilize the patient), latency and analgesic scales appropriate to the cognitive state of the study sample.

3. HYPOTHESES AND OBJECTIVES

3.1. HYPOTHESIS:

Levobupivacaine has advantages over Ropivacaine in the combined blockade (PENG - pericapsular nerve group- and the femoral lateral cutaneous nerve -BNFCL-) in hip fractures of the elderly, since a better analgesic control, similar latency period, and a longer analgesic duration are obtained.

3.2. OBJECTIVES:

3.2.1. MAIN:

- To compare the analgesic efficacy of both local anaesthetics in the regional blockade of hip fracture surgery.

3.2.2. SECONDARY:

- To describe the behavior of this combined technique in hip fractures, establishing latency of onset and duration of analgesia.
- Describe the side effects derived from the described combined technique. To validate in our population, especially in patients with cognitive impairment, the usefulness of the analgesic scales chosen.

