6.7. MEASUREMENTS

- Demographic variables: age, sex, weight, height, comorbidity (ASA grade).
- Variables related to the injury: subcapital fracture, pectrochanteric, subpectrochanteric or others.
- Variables related to the type of surgery: partial hip arthroplasty, endomedullary nailing or others. Duration of surgery.
- Variables related to the response:
 - Latency: evaluated by analgesic scales up to 10 minutes.
 - Analgesic scales: EVN, Algoplus and PAINAD at rest and in activity. They will be carried out upon the patient's arrival at the operating room, continuous until 10 minutes after the nerve block, in the sedation for the subarachnoid block, when they are discharged from the URPA, and at 6, 12, 24 h after the realization of the block, and end of effect after the realization of the block.
 - Need and rescue drugs: rescue analgesia will be scheduled for the hospitalization floor, in case it is necessary. The need, drug and time of administration regarding the realization of the blockade will be collected (Annex II).

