6.10. STATISTICAL ANALYSIS

A descriptive analysis of the variables collected will be carried out. Non-categorical ones shall be expressed as median +/- IQR (interquartile amplitude). Categorical variables shall be expressed as percentages or frequencies.

After performing the relevant normality tests (Kolmogorov-Smirnov or Shapiro-Wilk), the sample differences will be determined by t-Student or Mann-Whitney U tests. In the comparison of pain scales we will use the analysis of variance (ANOVA or Kruskal-Wallis).

The comparative analysis of the categorical variables will be carried out by means of Chi-square tests with cross tables.

The control of the possible intermediate and confusing variables will be carried out by means of Multiple Linear Regression Analysis.

The significance level will be, by default, 5% (p<0.05).

All calculations will be carried out with the statistical program SPSS[®] 25.0 for Mac.

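### The aim of validating the pain scales cannot be met for cognitively impaired patients, because baseline cognitive status is not recorded; for the whole sample, the listed scale analysis cannot show that the scales measure the same thing

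*Combined protocol and SAP*

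**What the plan says.** The validation aim appears twice. Section 3.2.2 lists as a secondary objective "To validate in our population, especially in patients with cognitive impairment, the usefulness of the analgesic scales chosen". Section 2.1 says that "it is intended to validate the assessment of pain in the elderly by combining three scales: EVN, Algoplus, PAINAD". Section 2.3 adds that the trial needs "analgesic scales appropriate to the cognitive state of the study sample".

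For data, section 6.7 gives "Demographic variables: age, sex, weight, height, comorbidity (ASA grade" and, for pain, "Analgesic scales: EVN, Algoplus and PAINAD at rest and in activity" at a series of time points. Annex III has rows for the three scales at arrival, on sitting, at discharge from recovery, at 6, 12 and 24 h, and at the end of the block.

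For analysis, section 6.10 states: "In the comparison of pain scales we will use the analysis of variance (ANOVA or Kruskal-Wallis". It also names t or Mann-Whitney tests, chi-square tests for categorical variables, and regression for another purpose: "The control of the possible intermediate and confusing variables will be carried out by means of Multiple Linear Regression Analysis".

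**The concern.** An objective that singles out a subgroup needs a variable that defines it, and an objective to validate instruments needs an analysis that bears on validity. The plan supplies the scores but neither of these.

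If it is followed as written, nothing can be said about how the scales behave in cognitively impaired patients. Nor could anyone report how many such patients entered, or how many were lost because a scale could not be scored. For the whole sample, the one listed method could find no difference, or a clear difference, whether or not the scales track the same pain. Cognitive status retrieved after the event would be unplanned and, in an open-label trial (section 4), collected with outcomes known.

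**Working it through.** **1. The objective against the data items.** The check is whether any planned item identifies a cognitively impaired patient at baseline.

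- Section 6.7, demographic items: age, sex, weight, height, ASA grade. None is cognitive.
- Section 6.7, other items: fracture type, surgery type and duration, latency, scale scores, rescue. None is cognitive.
- Annex III: delirium is the nearest row. It stands among the complications and is not baseline status.
- PAINAD scores pain and does not classify cognition.
- Section 6.14.1 names the medical record as source, but no section plans to extract a cognitive diagnosis from it.

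No planned field defines the subgroup.

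**2. The objective against the methods.** Sections 6.10 and 6.11 contain no correlation, agreement, reliability or responsiveness analysis and no analysis by cognitive status.

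To see what a location test says about validity, one-way ANOVA was simulated across three scales in 97 patients (108 × 0.9 = 97.2). The score distributions are assumed.

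- Equal means of 4, SD 2, correlation 0: ANOVA rejected in 4.75% of 4,000 runs. Unrelated scales looked alike in about 95% of runs.
- Equal means, correlation 0.9: it rejected in 0% of 4,000 runs. One-way ANOVA ignores the pairing, so it is conservative here.
- Correlation 0.9, with one scale at mean 2 and SD 1 and the others at mean 4 and SD 2: it rejected in 100% of 1,000 runs.

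The result follows the means and does not distinguish related from unrelated scales.

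**3. Achievable precision.** The plan gives no precision target for this objective. Its 108 patients are sized on block duration (section 6.9), so there is no figure to reproduce. Inputs: 108 patients and 10% losses (section 6.9), leaving 108/1.1 ≈ 98 or 108 × 0.9 ≈ 97. The correlation and the subgroup size are assumptions.

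Formula: z = atanh(r), SE = 1/√(n − 3), limits = tanh(z ± 1.96 × SE).

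For r = 0.70, z = 0.867:

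- n = 98: SE = 1/√95 = 0.103; 0.867 ± 0.201; interval 0.58 to 0.79.
- n = 30: SE = 1/√27 = 0.192; 0.867 ± 0.377; interval 0.45 to 0.85.

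The documents give no prevalence of impairment. If 10% to 40% of 97 are impaired, the subgroup is 10 to 39 patients:

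| n | r = 0.6 | r = 0.8 |
|---|---|---|
| 10 | −0.05 to 0.89 | 0.34 to 0.95 |
| 19 | 0.20 to 0.83 | 0.54 to 0.92 |
| 29 | 0.30 to 0.79 | 0.61 to 0.90 |
| 39 | 0.35 to 0.77 | 0.65 to 0.89 |
| 97 (all) | 0.46 to 0.71 | 0.71 to 0.86 |

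The formula is the standard one for Pearson correlation and only approximate for Spearman. The table shows what the added field would allow, not the size of an error.

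**The case against.** A reader might infer that the whole objective is unanswerable. The documents do not support that. The objective covers the trial population, with impaired patients as its emphasis, and section 6.7 plans all three scales in the same patient, so whole-sample correlations can be computed. Even for the subgroup, a diagnosis may exist in the medical record; retrieving it is unplanned, not shown to be impossible.

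A reader might also infer that ANOVA or Kruskal-Wallis cannot show a response to treatment. That is too strong. Section 6.10 does not say which groups are compared, and a comparison of a scale before and after the block is a test of change.

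Nor do the documents say that the ANOVA is meant as the validation analysis. Section 1.14 lists the scale scores as a secondary variable, and the sentence may simply describe their comparison. On that reading, however, no analysis is assigned to the validation objective at all.

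Finally, it could be said that impaired patients are kept out anyway. Section 6.3 requires the patient to understand the consent, and section 6.6 withdraws patients whose scales cannot be evaluated. But sections 6.8 and 7 allow consent by a guardian or representative, so entry is possible. These rules make it more important to record who entered and who was lost.

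It stands that this is the last secondary objective, is absent from the summary's list of objectives, and does not touch the primary endpoint, randomisation or safety.

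**Conclusion.** The concern holds in a limited form. For cognitively impaired patients the objective cannot be met as planned, because no planned field identifies them. For the whole sample the data exist, but the listed scale analysis compares location and is not evidence that the scales measure the same thing.

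This conclusion rests on the text of sections 3.2.2, 6.7 and 6.10 and Annex III, and on no assumed figure. The numerical illustration does rest on assumed correlations and subgroup sizes. It shows usable precision in the whole sample and wide intervals in a subgroup of 10 to 39, which supports a descriptive analysis only. The point deserves correction because the remedy is cheap; it does not threaten the main comparison.

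**What to change.** Add one field to section 6.7 and Annex III: cognitive impairment documented in the medical record before surgery (yes/no).

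In section 6.10, prespecify the following overall and by cognitive status, with 95% confidence intervals for the estimates:

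- Spearman correlation of Algoplus with PAINAD at each common time point in all patients. This is the only between-scale check available in patients who cannot self-report.
- Spearman correlation of EVN with Algoplus and with PAINAD in patients able to self-report.
- Responsiveness of each scale as within-patient change from arrival to sitting, for which Annex III already has rows for all three scales. State whether the scores are at rest or in activity, since section 6.7 asks for both and Annex III does not separate them.
- The number of patients for whom each scale could not be completed, or who were withdrawn for that reason under section 6.6.

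If change to 10 minutes after the block is preferred, Annex III needs a row for all three scales at that time. Section 6.7 (three scales up to 10 minutes) and section 6.8 (only the numerical scale and Algoplus at the latency check) would then have to be reconciled.

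Keep ANOVA or Kruskal-Wallis for comparing scores, but do not present it as evidence of validity. If the field is not added, drop the cognitive-impairment part of the objective.

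The cost is one or two form rows and a short paragraph of analysis. The cognitive field comes from the existing record and needs no new patient procedure, so it leaves the low-intervention basis in section 5 alone. The limitation is a small impaired subgroup of unknown size, whose results are descriptive only.
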